6.4. Treatment Compliance

Summaries of study treatment exposure and dose modifications (e.g., number of dose reductions, number of dose interruptions) will further characterize compliance. These analyses are described in Section 6.5 'Extent of Exposure'.

6.5. Extent of Exposure

Extent of exposure to GSK2857916 will be summarized.

The number of cycles administered to study treatment will be summarised with mean, median, standard deviation, minimum, and maximum. The number and percentage of subjects who received a given number of cycles (<4, 4, and >4 cycles) will be reported.

Dose intensity (dose delivered per cycle) will be summarized using mean, median, standard deviation, minimum, and maximum by cycle and overall. Dose intensity is the cumulative actual dose divided by the total number of cycles across the entire treatment period. A by subject summary listing of data on exposure to all study treatments will be produced.

Dose reductions will be summarised by number of reductions and reasons for reductions. Dose delays will be summarised by number of delays, reasons for the delays, and delay duration (days). The number and percentage of the delays 1-21, 22-42 and >42 days will be computed. Primary reasons for dose reductions and dose delays will also be summarized by cycle.

Duration of delays is defined as period from the expected start date of dose to actual start date of current dose. Calculation: (actual start date of current dose - expected start date of dose). Expected start date of dose = actual start date of previous dose + 21.

The summaries of dose modifications will be provided only if the data warrant.

All the dose reductions, dose escalations, infusion interruptions, incomplete infusions and dose delays will be listed separately.

A plot showing the number and percentage of subjects treated at different dose levels over time will be provided.

The duration of exposure to study treatment in days (from first day to last day of treatment) will be calculated. A horizontal bar graph of duration of treatment will be produced that displays duration of treatment in days for each subject.

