2.2. Study Objective(s) and Endpoint(s)

Objectives	Endpoints
Primary Objectives	Primary Endpoints

 To determine safety, tolerability, maximum tolerated dose (MTD), and recommended phase (RP2) dose and schedule of GSK2857916 administered 	
 Adverse events (AE) and changes in clinical signs and laboratory parameters
Secondary Objectives	Secondary Endpoints

 To evaluate the pharmacokinetic (PK) profile of GSK2857916 and the breakdown product cys-mcMMAF after intravenous (IV) single and repeat dose administration in subjects with relapsed/refractory MM and BCMA expressing lymphomas 	
 GSK2857916 and cys-mcMMAF PK parameters following IV single and repeat dose administration during dose escalation as data permit (e.g., AUCs C_{max}, t_{max}, CL, V_{ss}, t_{1/2} [single dose], C_{max} and C_{trough} [repeat dose]). GSK2857916 population PK parameters in expansion cohorts at the RP2 dose (e.g. clearance (CL), volume of distribution (V_d)), and relevant covariates which may influence exposure (e.g. age, weight, or disease-related covariates e.g. BCMA expression)

 To assess anti-drug antibody (ADA) formation after IV single and repeat dose administration of GSK2857916 	
 ADA incidence and titers after single and repeat IV dosing of GSK2857916

 To explore the initial anti-tumor activity of GSK2857916 in subjects with relapsed/refractory MM and BCMA expressing lymphomas 	
 Clinical activity measured as Overall Response Rate (ORR) which is defined as follows: 
 For MM: the percentage of subjects achieving confirmed partial response or better (≥PR) In addition, the percentage of subjects with minimal response (MR) will be assessed for clinical benefit rate (CBR) (Appendix 1 of protocol) For Lymphomas: the percentage of subjects achieving PR or better (≥PR) (Appendix 2 of protocol)
Exploratory Objectives	Exploratory Endpoints

 To evaluate PD markers in MM after treatment with GSK2857916 	
 sBCMA levels, BCMA receptor occupancy and cell death markers in subjects with MM.

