2.3. Study Design

Overview of Study Design and Key Features	
Dosing	
 • Part 1 Dose Escalation Initially, GSK2857916 will be administered (IV) via 60 min infusion once every three weeks (21 days = 1 cycle) on Schedule 1. Once an MTD1 or RP2D has been established on the once every 21-day (Schedule 1), the safety, tolerability, PK, and PD of once-weekly dosing (Schedule 2) of GSK2857916 may be explored as an additional cohort(s). • Part 2: Dose Expansion Phase Subjects enrolled in Part 2 dose expansion phase will be administered GSK2857916 at recommended phase 2 dose (RP2D) established based on Part 1 outcomes.
Time & Events	
 • Refer to Appendix 2: Schedule of Activities
Treatment Assignment	
 • This is a non-randomized open-label study.
Interim Analysis	
 • Part 1: Dose Escalation Phase No formal interim analysis is planned for Part 1. Safety, pharmacokinetic and pharmacodynamic marker data will be examined on an ongoing basis to support dose escalation decisions. • Part 2: Dose Expansion Phase 
 ○ For MM cohort, one futility analysis based on ORR data was performed after approximately 30 subjects are evaluable (originally 3 futility analyses are planned after approximately 15, 22 and 30 subjects are evaluable). The number of confirmed responses (PR or better) observed will be compared with the stopping rules provided in Section 13.6.2 of the protocol. ○ For the lymphomas expressing BCMA cohort, no interim analyses will be performed, though consideration would be given to closing the cohort should the enrolment be stopped in the MM cohort.

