16.6.2. Study Population

Extent of Exposure

 • Number of days of exposure to study drug will be calculated based on the formula: Duration of Exposure in Days = Treatment Stop Date - (Treatment Start Date) + 1 • Participants who were randomized but did not report a treatment start date will be categorised as having zero days of exposure. • The cumulative dose will be based on the formula: Cumulative Dose = Sum of Dose at Each Cycle • Dose intensity per cycle will be based on the formula: Dose intensity Per Cycle = Cumulative Dose / Total Number of Cycles

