1.0513	All Treated	OSP2	Summary of Prior Cancer and Non-Cancer Related Surgical Procedures (Part 2 NHL)	Report for: Part 2 NHL, (Summarize: only for 3.4 NHL).	SAC
Exposure and Treatment Compliance					
1.0240	All Treated	OEX5	Summary of Exposure to GSK2857916 (Part 1)	Report for population: Part 1, (Summarize: by ascending dose level, Total). Do not need "Dose Intensity "	SAC [A]

CONFIDENTIAL

BMA117159

Study Population Tables					
No.	Population	IDSL / Example Shell	Title	Programming Notes	Deliverable [Priority]
				section. Use 4, <4, >4 cycles	
1.0241	All Treated	OEX5	Summary of Exposure to GSK2857916 (Part 2 MM)	Report for population: Part 2 MM, (Summarize: only for 3.4 MM). Do not need "Dose Intensity " section. Use 4, <4, >4 cycles	SAC [A]
1.0242	All Treated	OEX5	Summary of Exposure to GSK2857916 (All Treated MM)	Report for population: All Treated MM, (Summarize: Total) Do not need "Dose Intensity " section. Use 4, <4, >4 cycles	SAC [A]
1.0243	All Treated	OEX5	Summary of Exposure to GSK2857916 (Part 2 NHL)	Report for population: 3.4 NHL, (Summarize: Total) Do not need "Dose Intensity " section. Use 4, <4, >4 cycles	SAC
1.0230	All Treated	OEX6	Summary of Dose Intensity of GSK2857916 by Cycle (Part 1)	Report for: Part 1, (Summarize: by ascending dose level, Total). Dose Intensity(mg/kg/cycle)	SAC [A]
1.0231	All Treated	OEX6	Summary of Dose Intensity of GSK2857916 by Cycle (Part 2 MM)	Report for: Part 2 MM, (Summarize: only for 3.4 MM). Dose Intensity(mg/kg/cycle)	SAC [A]
1.0232	All Treated	OEX6	Summary of Dose Intensity of GSK2857916 by Cycle (All Treated MM)	Report for: All Treated MM, (Summarize: Total). Dose Intensity(mg/kg/cycle)	SAC [A]
1.0233	All Treated	OEX6	Summary of Dose Intensity of GSK2857916 by Cycle (Part 2 NHL)	Report for: Part 2 NHL, (Summarize: only for 3.4 NHL). Dose Intensity(mg/kg/cycle)	SAC

CONFIDENTIAL

BMA117159

Study Population Tables					
No.	Population	IDSL / Example Shell	Title	Programming Notes	Deliverable [Priority]
1.0250	All Treated	ODMOD 1	Summary of Dose Reductions of GSK2857916 (Part 1)	Report for: Part 1, (Summarize: by ascending dose level, Total).	SAC [A]
1.0251	All Treated	ODMOD 1	Summary of Dose Reductions of GSK2857916 (Part 2 MM)	Report for: Part 2 MM, (Summarize: only for 3.4 MM).	SAC [A]
1.0252	All Treated	ODMOD 1	Summary of Dose Reductions of GSK2857916 (All Treated MM)	Report for: All Treated MM, (Summarize: Total).	SAC [A]

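### Dose intensity is defined per cycle with no time term, so dose delays do not lower it, and no planned summary gives dose delivered per elapsed time

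*SAP*

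**What the plan says.** SAP Section 6.5 introduces the measure with "Dose intensity (dose delivered per cycle) will be summarized using mean, median, standard deviation, minimum, and maximum by cycle and overall" and then defines it: "Dose intensity is the cumulative actual dose divided by the total number of cycles across the entire treatment period". Section 16.6.2 repeats this as "Dose intensity Per Cycle = Cumulative Dose / Total Number of Cycles", with the numerator given by "Cumulative Dose = Sum of Dose at Each Cycle". Tables 1.0230-1.0233 report it by cycle, in mg/kg/cycle.

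The planned interval is fixed in Section 2.3: "once every three weeks (21 days = 1 cycle) on Schedule 1". Delays are handled apart from dose intensity. Section 6.5 measures each one against a date that moves with the previous dose, "Expected start date of dose = actual start date of previous dose + 21", and bands the durations as 1-21, 22-42 and more than 42 days. The display list carries these delay outputs:

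- Tables 1.0260-1.0263: delays
- Tables 1.0280-1.0283: primary reasons for delay by cycle
- Tables 3.0140-3.0143: adverse events leading to interruption or delay
- Tables 3.0160-3.0163: corneal events leading to interruption or delay
- Listings 1.0110-1.0111: delays by subject

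Section 6.5 makes the dose-modification summaries depend on whether the data justify them. It puts no such condition on the listings.

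**The concern.** The primary objective in Section 2.2 covers schedule as well as dose: "To determine safety, tolerability, maximum tolerated dose (MTD), and recommended phase (RP2) dose and schedule of GSK2857916 administered". Section 6.4 sends the reader to the exposure and dose-modification summaries of Section 6.5 for compliance.

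In oncology reporting, dose intensity is commonly read as delivery against the planned schedule. The quantity defined here has no time in its denominator. A subject whose toxicity is managed by lowering the dose shows a lower value. A subject whose toxicity is managed by waiting, and who is then dosed again in full, shows the full assigned dose. Someone who reads Tables 1.0230-1.0233 alone could conclude that delivery was close to plan when the amount received per three weeks was well below it.

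**Working it through.** The SAP states no dose-intensity value, so there is no figure to reproduce. The check applies the plan's formula and a time-based formula to the same assumed dosing histories.

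**Inputs from the SAP**
- Planned interval: 21 days (Section 2.3).
- Part 2 starting dose: 3.40 mg/kg (Section 5.1).
- Dose intensity: cumulative dose / number of cycles (Sections 6.5 and 16.6.2).
- Duration of exposure: stop date - start date + 1 (Section 16.6.2).

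**Assumptions**
- Six doses, all at 3.4 mg/kg, so the cumulative dose is 6 × 3.4 = 20.4 mg/kg.
- Cycles means cycles given. The SAP does not define the count. The gloss in Section 6.5 (dose delivered in a cycle) and its summary of cycles administered both point this way.
- Each delay is counted from the previous actual dose plus 21 days, as in Section 6.5. The first dose cannot be late.
- The delay patterns are illustrative. The SAP gives no delay rate.

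**Formulas**
- Plan: 20.4 / 6 = 3.40 mg/kg/cycle in every row below.
- Time-based: cumulative dose / ((last dose date - first dose date + 21) / 21), which counts the last cycle as 21 days.

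| History (6 doses) | First to last dose, days | 21-day periods | Dose per 21 days, mg/kg | % of 3.4 | Plan's figure |
|---|---|---|---|---|---|
| On time | 5 × 21 = 105 | 126/21 = 6 | 20.4/6 = 3.40 | 100 | 3.40 |
| Three 21-day delays | 105 + 63 = 168 | 189/21 = 9 | 20.4/9 = 2.27 | 67 | 3.40 |
| Every later dose 21 days late | 5 × 42 = 210 | 231/21 = 11 | 20.4/11 = 1.85 | 55 | 3.40 |
| Every later dose 42 days late | 5 × 63 = 315 | 336/21 = 16 | 20.4/16 = 1.275, rounded to 1.28 | 38 | 3.40 |

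**Contrast with a reduction.** Take three doses at 3.4 and three at 2.5 mg/kg, all on time; the 2.5 is chosen only to show the arithmetic. The total is 10.2 + 7.5 = 17.7, and 17.7/6 = 2.95 under both formulas. The plan's measure therefore responds to reductions and is blind to delays.

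**What the plan's other outputs show for the same rows.** The delay derivation returns 0, 21 or 42 days per dose as appropriate. Duration of exposure is 106, 169, 211 and 316 days. The histories are separable in the planned output, but not through dose intensity, and no listed summary divides dose by elapsed time.

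**The case against.** The strongest reply is that the measure is openly described as dose per cycle and that lateness is reported in detail elsewhere. That stands. A reader might infer that dose intensity is the plan's main exposure measure, or that the plan cannot show whether the three-weekly schedule was kept. The SAP supports neither. Section 6.5 does not rank the measures and begins with number of cycles. The exposure tables (1.0240-1.0243) explicitly omit the dose-intensity section. The delay tables, the tables of adverse events and corneal events leading to delay, and the delay listings show directly whether doses were late and why.

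A reader might also say that nothing in the plan combines dose and time. That is too broad. Listings 30.0130-30.0131 give overall exposure together with dose modifications for each subject. The footnote to the profile-plot shell for Figures 13.0190-13.0191 indicates that the plots mark reductions and delays. The exposure-response datasets in Section 16.10.1 derive a time-averaged AUC per day, although that analysis is reported separately.

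These outputs do not replace the missing statistic. The delay bands in Section 6.5 count delays, and the section specifies no total delay per subject. Figure 11.0020 plots dose level by cycle, so it does not show delay. Duration of exposure mixes delay with number of doses. The delay summaries are conditional in Section 6.5, although the listings are not.

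Nor are the delay bands evidence that the sponsor expects long delays. They are open-ended reporting categories. Resetting the expected date after each dose is an ordinary way to measure a single delay, and it does not enter the dose-intensity formula.

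**Conclusion.** The point holds in a narrow form. As defined, dose intensity reflects reductions and not delays, and no planned summary gives dose per elapsed time or relative to the assigned schedule. In the six-dose illustrations the plan's figure stays at 3.40, while the time-based value is 2.27, 1.85 or 1.28 mg/kg per 21 days (67%, 55% or 38%).

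Two assumptions carry this: that the denominator is cycles given, which the SAP implies but does not define, and that the delay histories are hypothetical. One could quote 50% and 33% for 21- and 42-day delays, from 3.4 × 21/(21 + delay) = 1.70 and 1.13. Those are long-run limits. They treat every cycle as lengthened, and they overstate the shortfall for six doses, where the first dose cannot be late and the last cycle counts as 21 days.

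This is a minor reporting matter. No efficacy result and no dose-escalation decision depends on it. It is worth changing because the objective names schedule and the remedy is cheap.

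**What to change.** In Sections 6.5 and 16.6.2 and in Tables 1.0230-1.0233:

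1. Add overall dose intensity = cumulative actual dose (mg/kg) / ((last dose date - first dose date + 21)/21), in mg/kg per 21 days.
2. Add relative dose intensity = 100 × that value / the assigned starting dose per 21 days.
3. Keep the present quantity, relabel it mean dose per infusion, and state that its denominator is the number of cycles given.

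The cost is SAP wording and one derived variable, with its percentage. The doses and dose dates already feed the planned cumulative-dose and delay derivations. The reported figure will be less favourable wherever delays occur. The formula has one limit that should be footnoted: time after the last dose counts as 21 days, so a longer hold that ends in discontinuation without another dose is not captured. The delay and discontinuation displays should stay alongside it.

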6.6. Concomitant Medications

Concomitant medications will be coded using GSK Drug coding dictionary, summarized, and listed. The summary of concomitant medications will show the number and percentage of subjects taking concomitant medications by Ingredient. Multi-ingredient products will be summarized by their separate ingredients rather than as a combination of ingredients. Anatomical Therapeutic Chemical (ATC) classification Level 1 (Body System) information will be included in the dataset created but will not appear on the listing or summary.

Prophylactic Medication for Infusion-Related Reactions will be summarized by drug class and drug name and listed separately. Eye medications will be listed.

In the summary of concomitant medications, each subject is counted once within each unique ingredient. For example, if a subject takes Amoxicillin on two separate occasions, the subject is counted only once under the ingredient "Amoxicillin". In the summary of concomitant medications, the ingredients will be summarized by the base only, using CMBASECD and CMBASE. Note: In order to be considered a concomitant medication, the concomitant medication must have been taken at some point during the on-therapy window.

Blood products or blood supportive care products with onset date within the on-therapy window will be included in the summary tables. The frequency and percentage of subjects using blood products and blood supportive care products after the start of study medication will be provided. Supporting listings will also be provided.

6.7. Subsequent Anti-Cancer Therapies

The number and percentage of subjects that received chemotherapy, immunotherapy, hormonal therapy, biologic therapy, radioactive therapy, small molecule targeted therapy, as post study treatment anti-cancer therapy will be summarized. Time from study treatment discontinuation to the first post study treatment anti-cancer therapy will also be included in this summary table.

Follow-up anti-cancer therapy will be coded using GSK Drug coding dictionary, then summarized by ingredient. A listing of the type of follow-up anti-cancer therapy received (chemotherapy, immunotherapy, hormonal therapy, biologic therapy, radioactive therapy, and small molecule targeted therapy for each subject will be provided).

7. EFFICACY ANALYSES

7.1. Primary Efficacy Analyses

No primary efficacy analyses were planned.

7.2. Secondary Efficacy Analyses

Details of the planned displays are provided in [Appendix 12](#): List of Data Displays and will be based on GSK data standards and statistical principles.

Unless otherwise specified, endpoints / variables defined in Section [7.2.1.1](#) and Section [7.2.2.1](#) will be summarised using descriptive statistics, graphically presented (where appropriate) and listed.

7.2.1. Multiple Myeloma

7.2.1.1. Endpoint / Variables

7.2.1.1.1. Overall Response Rate

Overall Response Rate (ORR), is defined as the percentage of responders (subjects with confirmed stringent complete response (sCR), complete response (CR), very good partial response (VGPR), and partial response (PR) as assessed according to 2011 International Myeloma Working Group (IMWG) criteria (Appendix 1 in the protocol)). Only the assessments from the start of treatment up to the earlier of disease progression or the start of new anti-cancer therapy will be considered. Only new systemic anti-cancer drugs taken are considered as anti-cancer therapy (radiotherapy and surgeries are not considered as systemic anti-cancer therapy for the purpose of this analysis). .

Subjects with only one assessment (therefore not confirmed), or assessments of Not Evaluable or missing response will be treated as non-responders; i.e. they will be included in the denominator when calculating the percentage.

7.2.1.1.2. Response Confirmation Algorithm

The definitions and details to derive unconfirmed and confirmed response are outlined below. For both confirmed and unconfirmed response derivations, only responses assessments from the start of treatment up to the earlier of disease progression or the start of new anti-cancer therapy will be considered. Date associated with response was defined in Section [16.5.5](#)

Definitions:

1. The hierarchy of response classifications from high to low is as following: sCR, CR, VGPR, PR, MR, SD, PD and NE. Response was assessed according to the 2011 Uniform Criteria Consensus recommendations of the International Myeloma Working Group (See Appendix 1 of protocol).

2. Definition of two consecutive assessments: the two consecutive assessments should be taken from two different samples, and NOT based upon the splitting of a single sample.
 - a. No minimum time separation between two consecutive assessments is required to confirm response.
 - b. If there are two assessments separated by not evaluable (NE) or Missing assessment(s), collapse data by ignoring NE or Missing assessments.
 - c. If two consecutive assessments are on different dates, it is assumed that the two assessments are from different samples
 - d. If there are multiple assessments on the same date and there is no data to show that they are from different samples, it is assumed these assessments are from the same sample. Then only the response with the lowest magnitude will be selected as the response for that date.

Two-step algorithm for determining the best confirmed response

Step1. Determine the confirmed response sequentially at each time of disease assessment.

- A. For confirmed sCR, CR, VGPR, PR, MR, SD, two consecutive assessments are required.
 - a. For any two consecutive assessments with different magnitudes, the confirmed response is the response of lower magnitude.
 - b. For any two consecutive assessments with the same magnitude, the confirmed response is the response of that magnitude.
 - c. Although the response will be confirmed at the time of the second one of the two consecutive assessments, the date of the first one of the two consecutive assessments will be the date of this confirmed response.

Table 4 Summary of the criteria for confirmation of sCR, CR, VGPR, PR, MR, SD

Response at one time-point of two consecutive assessments	Response at the other time-point of two consecutive assessments	Confirmed Response
sCR/CR/VGPR/PR/MR/SD	SD	SD
sCR/CR/VGPR/PR/MR	MR	MR
sCR/CR/VGPR/PR	PR	PR
sCR/CR/VGPR	VGPR	VGPR
sCR/CR	CR	CR
sCR	sCR	sCR

- B. For PD, since for this study, no confirmation of PD is required, only one PD assessment is required. Any PD assessment will be confirmed by itself at the time of the PD's assessment.
- C. If the subject has only one non-PD /non-NE assessment then the confirmed response is NE at the date of that assessment.
- D. If all assessments were NE then the confirmed response is NE at the date for each assessment.

Step 2. Determine the best overall confirmed response in Step 1. If assessments at all visits are missing then the best confirmed response is NE.

Examples:

Example 1.

Step1.

Visit	Response	Confirmed response
1	PR	
2	SD	SD
3	SD	SD

Step 2.

The best overall confirmed response is SD

Example 2.

Step1.

Visit	Response	Confirmed response
1	VGPR	
2	NE	
3	NE	
4	PR	PR

Step 2.

The best overall confirmed response is PR

Example 3.

Step1.

Visit	Response	Confirmed response
1	sCR	
2	sCR	sCR
3	CR	CR
4	PR	PR

Step 2.

The best overall confirmed response is sCR

Example 4.

Step1.

Visit	Response	Confirmed response
1	sCR	
2	CR	CR
3	CR	CR
4	PR	PR

Step 2.

The best overall confirmed response is CR

Example 5.

Step1.

Visit	Response	Confirmed response
1	CR	
2	VGPR	VGPR

Step 2.

The best overall confirmed response is VGPR.

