16.5.5. Date Associated with Response

Investigator assessment of disease is entered in the eCRF on the VISIT form. The date of the VISIT is captured but the date of the response assessment is not captured separately. The date associated with response will be the visit date for the VISIT on which the investigator assessed disease. A disease assessment may occur at an unscheduled visit. The date of the unscheduled visit would be assigned to any response assessed on that date. In the following section, unless otherwise specified, the disease assessment denotes post-baseline assessment.

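### The same-date rule in the MM response algorithm lets an NE record override an evaluable response, and leaves a same-date PD in conflict with Step 1B

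*SAP*

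**What the plan says.** SAP 7.2.1.1.2 opens its definitions with a ranking: "The hierarchy of response classifications from high to low is as following: sCR, CR, VGPR, PR, MR, SD, PD and NE". Definition 2 then sets out what counts as two consecutive assessments. Two of its sub-items matter here.

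- **2b** deals with NE or missing records that lie between two assessments. The instruction is to "collapse data by ignoring NE or Missing assessments".
- **2d** deals with records on one date. Its condition is: "If there are multiple assessments on the same date and there is no data to show that they are from different samples". Such records are taken to come from one sample, and the rule is: "Then only the response with the lowest magnitude will be selected as the response for that date".

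Step 1B of the same section treats progression separately: "Any PD assessment will be confirmed by itself at the time of the PD's assessment". SAP 7.2.1.1.1 limits the window for ORR: "Only the assessments from the start of treatment up to the earlier of disease progression or the start of new anti-cancer therapy will be considered".

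SAP 16.5.5 makes the visit date the response date, because no separate assessment date is captured. It adds: "A disease assessment may occur at an unscheduled visit", and "The date of the unscheduled visit would be assigned to any response assessed on that date".

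**The concern.** NE means that no response could be assessed. It is not a worse response than PD. Placing it last is right for Step 2, where the best response is picked and NE should win only if nothing else exists. In 2d the selection runs the other way: the lowest is kept, so the same ranking makes NE win over everything. A rule that looks meant to be conservative then discards the informative record and keeps the uninformative one.

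Two consequences follow. A discarded PR (or MR, or better) can remove half of a confirming pair. A discarded PD could leave the window open, so that later assessments count towards a confirmed response.

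Confirmed ORR and CBR come directly from this algorithm. So do the subjects who enter TTR, TTBR and DOR, the response dates used for TTR and TTBR, and the date from which DOR is measured.

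**Working it through.** There is no stated figure to reproduce, so the check applies the rules of 7.2.1.1.2 to short sequences. The inputs are the definition 1 order (sCR, CR, VGPR, PR, MR, SD, PD, NE), 2b, 2d, Steps 1A to 1C and Step 2, with the window closing at a PD.

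**Control.** Applied to the SAP's five worked examples, the rules give SD, PR, sCR, CR and VGPR, as printed. None of the five has two records on one date, so none settles how 2d treats NE.

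**Same-date selection under the definition 1 order.** Lowest of {PR, NE} = NE. Lowest of {PD, NE} = NE. Lowest of {PR, PD} = PD. Only the pairs containing NE misbehave.

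**Effect on best confirmed response.** Semicolons separate visits, and a plus sign marks records on one date with nothing to show different samples.

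| Sequence | 2d read literally | NE set aside first |
|---|---|---|
| PR; PR+NE | NE | PR |
| SD; PR; PR+NE; PD | SD | PR |
| PR; PR+NE; PR | PR, dated visit 1 | PR, dated visit 1 |
| SD; PR+NE; PR; PR | PR, dated visit 3 | PR, dated visit 2 |
| SD; PD+NE; PR; PR | PR, no PD retained | PD at visit 2 |
| PR; PD+NE; PR | PR, no PD retained | PD at visit 2 |
| SD; SD; PD+NE; SD | SD, no PD retained | SD, with PD at visit 3 |

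Row 1: only one evaluable record remains, so Step 1C returns NE. Row 2: the PR at visit 2 pairs only with the SD before it, so Step 1A gives SD. Row 3: 2b skips the NE, the two outer PRs pair, and nothing changes. Row 4: the response survives, but its date moves one visit later, because Step 1A dates a confirmed response at the first of the pair.

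The three PD rows depend on the order of the rules. If 2d selects the day's response before Step 1B is applied, the middle column holds. If Step 1B protects the PD regardless of 2d, the right-hand column holds. The SAP does not say which comes first.

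**Size per subject.** SAP 2.4 plans for 40 subjects in the Part 2 MM cohort. One reclassified subject changes ORR by 1/40 = 0.025, or 2.5 percentage points. It falls when a same-date PR is lost and rises if a same-date PD is dropped and later responses count.

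**The case against.** A reader might infer that the SAP deletes any progression that shares a date with an NE record. The text does not support that as a certainty. 2d sits under the definition of two consecutive assessments, and PD needs no second assessment. Step 1B speaks of any PD without qualification, and the cut-off at progression is stated outside the numbered definitions. On that reading the window closes at the PD whatever 2d selects. This stands: the PD half is a conflict between rules, not a proven deletion.

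It can also be argued that NE has no magnitude. Apart from 2d, the term is used only in Step 1A, which covers sCR to SD, and Table 4 has no NE row. But definition 1 ranks NE explicitly and no sentence takes it out of 2d. If magnitude were confined to sCR to SD, PD would drop out as well, and a same-date PR and PD would have no rule. That reading needs a correction too. Nor does 2b help, since it addresses NE between assessments, not NE sharing a date with one.

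Three limits stand in full. 2d applies only when no data show different samples, although for one date that is the SAP's default. The trigger is narrow: 16.5.5 allows assessments at unscheduled visits but does not say that two visits fall on one date. And a PR+NE date often does no harm, as row 3 shows.

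It would also be too broad to say that all of DOR depends on this algorithm. Its start and its membership do. Its end is documented progression or death due to PD, with the TTP censoring rules (7.3.1.2.3). Section 7.3.1.2.1 likewise bases PFS progression on the investigator's assessment, although the definition in 7.3.1.1 speaks of confirmed progression.

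**Conclusion.** Definition 2d is wrong as written for NE. With the only ranking the SAP provides, a same-date NE displaces an evaluable response. That can cost or re-date a confirmed response when the date is a necessary half of the pair. For a same-date PD, 2d and Step 1B give different answers and the SAP does not say which prevails.

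The impact is probably small and cannot be quantified, because the SAP gives no frequency of same-date pairs. The 2.5 points is the effect of one hypothetical subject at 40, not an estimate of bias. It reaches confirmed ORR and CBR, TTR, TTBR, and entry to and start of DOR. It does not clearly reach the progression dates for PFS, TTP or the end of DOR. ORR is a secondary endpoint summarised descriptively with an exact interval (7.2.1.2), and SAP 2.4 plans no hypothesis test for the Part 2 MM cohort, so no formal decision at the final analysis turns on it.

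The conclusion rests on taking magnitude in 2d to mean the definition 1 order, as no other order is given. It should still be corrected, because two programmers could derive different responses from the same records.

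**What to change.** Reword 2d along these lines: *Disregard NE and missing assessments when an evaluable assessment exists on the same date. Among those remaining, select the lowest of sCR to PD. Assign NE only if every assessment on that date is NE.* Add that a PD recorded on a date always stands under Step 1B and closes the assessment window. A sixth worked example with a same-date pair would remove any doubt.

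The cost is a sentence or two in the SAP and one line of code. No further data are needed, and subjects without same-date records are unaffected.
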